### **Subject Selection Criteria**

Women scheduled for office intra-detrusor chemodenervation with onabotulinum toxin A for a diagnosis of overactive bladder (OAB), urinary urgency (UU), or urgency urinary incontinence (UUI) based on subjective or objective data will be identified and screened against inclusion and exclusion criteria. If potential subjects meet the requirements for the study, they will be eligible to be invited for participation. Subjects will be consented for study enrollment by physicians, fellow physicians, and/or a delegated study team member on the day of their procedure.

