### **Inclusion Criteria**

- Non-pregnant females
- Age 18 years and older
- English as a primary language
- Scheduled for office intra-detrusor chemodenervation for diagnosis of OAB/UU/UUI
- Baseline visual analog scale for anxiety  $\geq 12\text{mm}$

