### **Sample Size**

Our sample size calculation was based on a prior study within the urogynecologic population which showed a statistically significant reduction in VAS-anxiety when aromatherapy was used during multichannel urodynamics, a common urogynecologic office procedure. With a sample size of  $n=80$  we would have 80% power to detect a mean clinically important difference of 12mm out of 100mm on the anxiety visual analog scale assuming a standard deviation of 18.8 and p-value 0.05. As the intervention is delivered at the week level, if we reach  $n=80$  early in the week, we will plan to finish out the week and thus may reach a total sample size slightly greater than 80, increasing statistical power.

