### **Interventions and Interactions**

Patients scheduled for office intra-detrusor chemodenervation will be contacted by study staff via phone to introduce the study and gauge interest in participating. Interested and eligible patients will be asked to arrive thirty minutes before their scheduled procedure time to complete the consent process. Upon arrival, patients will be escorted to a research office where informed consent will be obtained. After obtaining informed consent, all participants will fill out a pre-procedure visual analog scale (VAS) for

anxiety (Figure 1) and a VAS for pain (Figure 2). If all inclusion criteria are met, including VAS-anxiety  $\geq 12$ mm on 100mm scale, participants will be enrolled and then escorted to the procedure room.

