### **Intervention:**

#### **Group 1:** Intervention

- Lavender aromatherapy sticker on patient, procedure staff, MD lapel
- Calming music from Sirius XM station 68 (Spa) playing via overhead speakers
- Overhead lights off, two lanterns lit to provide dim lighting
- Avoid stirrup use

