#### **Group 2:** Control

- Non-aromatic (placebo) sticker on patient, procedure staff, MD lapel
- No music playing
- Overhead lights on
- Stirrups used

In order to create the least disruption to our clinical workflow, we propose randomizing the weeks of the study rather than randomizing participants. Permuted block randomization will be used such that a random sequence of blocks of 4 or 6 weeks (totaling to the number of weeks planned for the study) will be chosen. Within each block of 4 or 6 weeks, the weeks will be equally randomized to treatment or control. For example, within a four-week block, two of four weeks will be randomized treatment and two to control. Permuted block randomization will ensure that (i) prognostic factors (e.g., first-time vs. repeat patient) are balanced over the course of the study and (ii) seasonality is addressed (e.g., within summer, half of the weeks are control and half treatment). Each week of the study will be randomized to either Relaxing Environment Package or Typical Office Environment (control), rather than randomizing individual patients. On Monday of every week, an envelope will be opened to determine if it is a Relaxing Environment Package week or Control week. Randomization will be discussed in more detail below.

If the week is randomized to a *Relaxing Environment Package*, the patient, procedure staff, and MD will enter the procedure room and receive a lavender aromatherapy sticker to be worn on their lapels. The lavender aromatherapy sticker will be ordered from Aroma Stickers store website (<https://aroma-stickers.com>). Calming music from Sirius XM station 68 (Spa) will be playing softly in the background via overhead speakers. If the patient had planned to listen to their own music during the procedure, this will be permitted and documented. Procedure consent and preprocedural preparation (see below) will take place. The overhead lights will then be turned off, and two battery powered lanterns will be lit to provide dim lighting. Stirrups will be avoided, if possible, during the preparation and procedure.

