If the week is randomized to *Typical Office Environment*, the patient, procedure staff, and MD will enter the procedure room and receive a non-aromatic (placebo) sticker to be worn on their lapels. The non-aromatic sticker will be obtained from an office supply store. No music will be playing, and all of the lights will be on as is typical in our practice. Procedure consent and preprocedural preparation (see below) will take place. The lights may then be adjusted during cystoscopy per provider preference for adequate visualization.

To minimize lavender cross contamination and unintended topical or environmental exposure in those not participating in the study or with lavender allergy, we opted to use a lavender aromatherapy sticker rather than a diffuser. Unlike a diffuser, the aromatic sticker does not leave a scent in the air once the sticker is removed from the room. When the aromatic sticker is worn on a shirt lapel it can only be smelled at close distances, typically only by the individual wearing the sticker. Aromatic stickers will be maintained outside the procedure room in a sealed bag. If a patient is randomized to the Relaxing Environment Package, the stickers will be brought into the procedure room and distributed to patients and staff. The sticker will be placed on the subjects' shirt lapel. Once the procedure is completed the stickers will be recollected, placed back in the sealed bag, and disposed of by study staff. This will limit any environmental exposure to lavender for the next patient. Routine hand washing or sanitization by MD and procedure staff and routine cleaning of procedure room between patient encounters will limit any cross contamination or unintended topical exposure. For patients or staff not participating, we believe that lavender levels will not be above those expected in everyday life. Additionally, our office has a second procedure room that can be used for any patients with a lavender allergy.

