### **INFORMED CONSENT**

Signed informed consent will be obtained from each patient subject by a delegated study team member in-person on the day of the scheduled procedure.

Signed informed consent will be obtained from MD and procedure staff subjects by a delegated study team member prior to participation in any study procedures.

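### For every procedure after Monday the week's arm is open at the site before consent and the baseline anxiety score, and no rule withholds it until that score is recorded

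*Combined protocol and SAP*

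**What the plan says.** Allocation is by week. Under Group 2: Control, the protocol states: "On Monday of every week, an envelope will be opened to determine if it is a Relaxing Environment Package week or Control week". Subject Selection Criteria says: "Subjects will be consented for study enrollment by physicians, fellow physicians, and/or a delegated study team member on the day of their procedure". Informed Consent is narrower: "Signed informed consent will be obtained from each patient subject by a delegated study team member in-person on the day of the scheduled procedure". Before that day, patients are "contacted by study staff via phone to introduce the study and gauge interest in participating" (Interventions and Interactions); the timing of this call relative to the Monday opening is not given.

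VAS #1 is completed in the research office after consent. It is an entry criterion ("Baseline visual analog scale for anxiety" of at least 12 mm, Inclusion Criteria) and also the baseline from which the primary change score is measured (Primary Outcome Measure).

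The arm is visible to those who work in the procedure room. In intervention weeks there is a "Lavender aromatherapy sticker on patient, procedure staff, MD lapel"; in control weeks the same people wear a plain one. On the lavender stickers the protocol adds: "Once the procedure is completed the stickers will be recollected, placed back in the sealed bag, and disposed of by study staff".

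The Randomization section says that permuted blocks stop clinic staff from predicting weeks, that subjects, staff and investigators cannot be blinded, and that the statistician will be.

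**The concern.** Randomising weeks in permuted blocks protects allocation only while a week is still sealed. Once the envelope is open, one fact applies to every patient for the rest of that week. Anyone who knows it while inviting patients, taking consent or handing out VAS #1 could, without intending to, influence who enters or how the first score is marked.

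That score matters twice, because it decides entry and it is half of the primary endpoint. An arm-dependent influence on it would pass straight into the comparison of mean change. Three routes are possible:

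- the reported VAS #1 shifts with the arm;
- one arm in effect enrols from a higher reported score;
- one arm enrols patients whose underlying anxiety is higher.

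**Working it through.** **1. The plan's own figure.** Sample Size gives n = 80 for 80% power to detect 12 mm, "assuming a standard deviation of 18.8 and p-value 0.05". The normal formula gives, per arm, 2 × (1.960 + 0.842)² × 18.8² / 12² = 2 × 7.85 × 353.44 / 144 = 38.5, so 39 per arm and 78 in total. The t-test version gives 39.5, so 40 per arm and 80 in total, with power 0.805. The stated size is reproduced and is not in question. Below I use 40 per arm.

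**2. Order of events.**

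| Step | When | Where stated |
|---|---|---|
| Week's envelope opened | Monday | Group 2: Control |
| Consent | procedure day | Subject Selection Criteria; Informed Consent |
| VAS #1, then the 12 mm decision | procedure day, after consent | Interventions and Interactions; Primary Outcome Measure |
| Sticker, music, lighting | after entering the procedure room | Group 1; Group 2 |

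For any procedure from Tuesday on, the first step precedes the second and third. For Monday procedures the hour of opening is not given, so the order cannot be determined.

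**3. Who could know the arm.** The physician wears the sticker and may take consent. Study staff dispose of lavender stickers and collect the post-procedure pain score. Research staff record all data, and the paper data flow covers eligibility, baseline data and intervention group (Subject Recruitment Methods). The documents do not say whether these are the people who recruit.

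**4. What comes near to a safeguard.** The blocks cover only unopened weeks. The separate consent room delays exposure to the environment but is silent on disclosure. Table 1 lists randomization below VAS #1, which suggests the intended order; but there is no patient-level randomization, and a row order is not a disclosure rule. None of these withholds the arm after opening.

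**5. Conditional size.** From the documents: the 12 mm gate, 18.8 and 40 per arm. Assumed: no true effect; normal scores with equal SD; correlation r between VAS #1 and VAS #2 of 0.5 or 0.7; baseline mean 30 or 40 mm. Each score is a stable level plus independent occasion-to-occasion variation, with r the stable share of the variance. Entry requires a reported VAS #1 of at least 12 mm. The 0 and 100 limits and week clustering are not modelled. Sample Size does not say whether 18.8 belongs to a single score or to the change, so both readings are simulated.

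Two results follow directly. If VAS #1 shifts by d and VAS #2 does not, the baseline-adjusted bias is r × d: 0.5 × 5 = 2.5 mm and 0.7 × 5 = 3.5 mm. If selection is on the reported VAS #1 alone, the expected VAS #2 at a given VAS #1 is unchanged, so the adjusted bias is zero. Simulation supplies the rest (absolute bias in mm, range over the assumed means and correlations):

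| What differs in one arm | 18.8 = single-score SD: unadjusted / adjusted | 18.8 = change-score SD: unadjusted / adjusted |
|---|---|---|
| VAS #1 shifted by 5 mm | 3.90–4.71 / 2.46–3.50 | 3.92–4.57 / 2.45–3.55 |
| In effect enrols at 20 mm or more | 0.72–1.77 / about 0 | 0.93–1.82 / about 0 |
| Omits the 20% with lowest stable anxiety (cut applied before the gate) | 0.59–0.91 / 1.23–2.26 | 0.77–0.98 / 1.25–2.31 |

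The unadjusted shift is below 5 mm because the gate acts on the shifted score. A higher VAS #1 in intervention weeks would favour the package; a lower one would work against it. In the third row adjustment raises the bias, because selection on stable anxiety raises the expected VAS #2 at any given VAS #1.

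**The case against.** The strongest defence is that nothing in the documents shows disclosure. They do not say who opens the envelope or who is told. The consent pages are not in the copy reviewed, so what patients are told cannot be judged. The patient draws her own line, in a research office, before entering the procedure room, and stickers are handed out only in that room. All scheduled patients are to be approached, and reasons for screen failure are logged. Week allocation is a reasoned choice, made for clinic flow, fewer deviations and the assessment of team burnout.

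Much of this stands. It means that the 5 mm shift, the most damaging row of the table, needs the arm to reach the patient or influence the scoring, and that is possible but not shown. The selection rows are small against the 12 mm target, and the third depends on the assumed model and on where the cut is placed. It does not answer the point on sequence. That the treatment phase cannot be blinded says nothing about when the arm may be disclosed, and holding it back until VAS #1 is handed in is compatible with week allocation.

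A reader might infer that the trial's false-positive rate is inflated. With a standard error of 18.8 × √(2/40) = 4.20 mm, a 4 mm bias would indeed give 15.8% instead of 5%. But that 4 mm is an assumption, and no passage supports it as a property of this trial. A reader might also infer that withholding the arm from the patient closes every route. It does not, because selective enrolment acts through the recruiter.

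**Conclusion.** The point holds as a missing safeguard. For procedures after Monday the arm is open at the site before consent and before the score that serves as both gate and primary baseline, and no written rule withholds it. This follows from the text and needs no assumption.

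Bias is neither documented nor measurable from the documents, in size or direction. The illustrative values (about 4 to 5 mm unadjusted for a 5 mm shift in VAS #1; about 2 mm or less unadjusted for modest selective enrolment) rest on the assumed shift, selection rules, means and correlations, and should not be read as estimates. Baseline adjustment alone is not a full answer: it removes selection on the reported score, leaves 2.5 to 3.5 mm of a 5 mm shift, and can raise the bias from selection on underlying anxiety to about 1.2 to 2.3 mm. The change is worth making because it is cheap, not because harm has been shown.

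**What to change.** 1. State that the week's arm is not disclosed to the patient, and the intervention-group entry on the paper record is not completed, until VAS #1 is handed in and the 12 mm decision is recorded.
2. Amend Subject Selection Criteria to agree with Informed Consent, so that a delegated team member, not the physician or fellow doing that patient's procedure, handles consent, VAS #1 and the eligibility decision in the research office. Where existing staffing allows, that person is not told the arm.
3. Report the numbers approached, refused, screen-failed for VAS below 12 mm and enrolled, together with baseline VAS, by the week's arm.
4. Name baseline VAS-anxiety as a covariate in the primary regression. The Analytical Plan leaves covariates to be chosen as needed and does not mention it. This comes in addition to concealment, not in place of it.

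Item 1 closes the patient route only. Recruiter selection is closed only if the recruiter is also unaware of the arm; otherwise item 2 reduces it and item 3 makes it visible.

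Cost: items 1, 3 and 4 need wording, simple counts that build on the existing screen-failure log, and a score already collected. Item 2 uses a room and a role already in the protocol. Keeping that person wholly unaware of the arm could need separate staff; the documents give no staffing figures, so it is asked only where feasible. The downside is minor scheduling inconvenience, and the arm may still leak to study staff within a week.

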**Table 1. Patient Data Collection Schedule**

\*Other demographic data includes: Age (years), Race, Body Mass Index (BMI in kg/m^2), smoking status (current/former/never), insurance type (private/Medicare/Medicaid/None), use of aromatherapy at home in the last six months (yes/no)

\*\*Procedure data includes: first time injection (yes/no), repeat procedure (yes/no), time of patient entering room, time of VAS anxiety #2, protocol modifications (stirrups used, support person present, listening to personal music, other relaxation techniques used, etc)

	Baseline	Start of clinic day	End of clinic day
Informed Consent	x		
*Demographics	x		
Burnout Battery		x	x

**Table 2. MD and Procedure Staff Data Collection Schedule**

\*MD gender, MD years of experience performing office bladder chemodenervation, procedure staff gender, procedure staff years of experience supporting office procedures, MD and procedure staff use of aromatherapy at home in the last 6 months (yes/no)

## RANDOMIZATION

A permuted block randomization scheme will be used to assign weeks in a 1:1 ratio to intervention or control. The permuted blocks will prevent clinic staff from being able to predict which weeks will be Relaxing Environment Package or control. However, it will not be possible to blind subjects, staff, or investigators. Our statistician will be blinded. Randomization of weeks rather than patients was selected to minimize impact to clinic flow and help prevent protocol deviation among our busy clinic staff who often have back-to-back procedures. It will also allow assessment of procedure team burnout. Patients will only participate in the study once.

## OUTCOME MEASURES

### Primary Outcome Measure:

The primary outcome is to compare the mean change in patients' anxiety level from when they arrive for their procedure to their anxiety level after at least 10 minutes of exposure to the relaxing or typical office environment (while the lidocaine anesthetic is given time to work in the bladder). The mean change in anxiety levels will be compared between the intervention and control groups. Anxiety will be assessed using a visual analog scale (VAS) (Figure 1). The VAS for anxiety is a validated scale that ranges from 0-100mm^14. 0mm is equivalent to "no anxiety" and is located on the left. 100mm is equivalent to "extremely anxious" and is located on the right. Subjects are asked to draw a vertical line on the scale that corresponds to their level of anxiety. The first VAS anxiety score (baseline) will be collected the day of the procedure in the research office after obtaining consent. The second VAS anxiety score (after exposure) will be collected just prior to starting the procedure after at least 10 minutes of exposure to the procedure room environment. The minimum clinically important difference for VAS anxiety is a change of 12mm on a 100mm scale.

## Secondary Outcome Measures

**Procedure pain:** Pain during the chemodenervation procedure will be assessed using a visual analog scale for pain (Figure 2). The VAS for pain is a validated scale that ranges from 0-100mm^15. 0mm is equivalent to “no pain” and is located on the left. 100mm is equivalent to “worst possible pain” and is located on the right. Subjects are asked to draw a vertical line on the scale that corresponds to their level of pain during the procedure. Baseline scores will be collected on the day of the procedure in the research office after obtaining consent. Patients will then be asked to circle the pain scores that corresponded to the pain experienced during the procedure. This will be collected by study staff after the procedure once the patient is dressed.

**Satisfaction with experience:** Patient satisfaction with their procedure experience will be assessed using a visual analog scale for patient satisfaction (Figure 3). The VAS for patient satisfaction is a validated scale ranging from 0-100mm^16. 0mm is equivalent to “no satisfaction” and 100mm is equivalent to “extreme satisfaction”. Subjects are asked to draw a vertical line that corresponds to their level of satisfaction with their procedure experience.

**Procedure team burnout:** Procedure team burnout will be assessed using a Burnout Battery visual analog scale for healthcare worker burnout (Figure 4). This tool was created to assess the working energy states of healthcare providers and is correlated with the Maslach Burnout Inventory which is a validated 22 question survey regarding workplace burnout. The RN(s) assigned to chemodenervation procedures as well as the physician performing the procedure will fill out the Burnout Battery VAS at the beginning and end of the clinic day. Providers are asked to circle the battery that represents their current energy level.

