### **Secondary Objectives**

1. Determine if the Relaxing Environment Package reduces a patient's pain during office administration of intra-detrusor onabotulinum toxin A injections based on a visual analog scale.
2. Determine if the Relaxing Environment Package increases patient satisfaction with their procedure experience based on a visual analog scale.
3. Determine if the Relaxing Environment Package decreases procedure staff burnout based on a visual analog scale.

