All patients will receive routine preprocedural antibiotic prophylaxis, sterile urethral preparation with betadine or chlorhexidine, and 60cc viscous intravesical 1% lidocaine will be instilled into the bladder with sterile technique. After staying in the environment in the supine position with a sheet covering the lower half of their body and legs for at least 10 minutes while the local anesthetic takes effect, participants will then fill out a 2nd VAS for anxiety. The procedure will be performed, and any patient requested modifications to the protocol will be recorded. After the procedure and once participants are dressed, they will fill out a 2nd VAS for pain and a VAS for procedure satisfaction (Figure 3).

The procedure staff and MD will fill out the Burnout Battery visual analog scale (Figure 4) at the start of the day prior to seeing any patients. They will again complete the Burnout Battery visual analog scale at the day's conclusion, after seeing their last patient. They will also record how many chemodenervation procedures they participated in that day.

The electronic medical record, with participant permission, will be reviewed to establish patient demographics, indication for procedure, whether primary or repeat procedure, and medical history. Years of experience and demographic information of the procedure staff and MD will also be recorded.

	Baseline	Procedure	Post-procedure
Informed Consent	x		
Medical History	x		
Medication review	x		
*Other Demographics	x		
VAS Anxiety #1	x		
VAS Pain #1	x		
Randomization	x		
VAS Anxiety #2		x	
**Procedure		x	

VAS Pain #2			x
VAS Patient Satisfaction			x

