## ANALYTICAL PLAN

Descriptive statistics will be used to summarize baseline characteristics of treatment and control groups. Means and standard deviations (or medians and interquartile ranges) will be used to summarize continuous variables such as age, and frequencies and percentages will be used to summarize categorical variables such as first-time vs. repeat patient. Regression analyses will be performed to test the hypotheses about treatment effects on primary and secondary outcomes. Planned regression models can flexibly address missing data and include covariate adjustment for important prognostic variables (such as first-time vs. repeat patient), as necessary. Exploratory subgroup analyses will be performed to characterize treatment effects within groups of interest, such as first-time or repeat patients.

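### The procedure-pain paragraph gives two ways of recording the same reading (draw a line, circle scores); one mode, scored in mm, should be stated, with baseline pain as a covariate

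*Combined protocol and SAP*

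**What the plan says.** The first secondary objective is to learn whether the package "reduces a patient's pain during office administration of intra-detrusor onabotulinum toxin A injections based on a visual analog scale". Under Secondary Outcome Measures, the procedure-pain paragraph names the instrument: "The VAS for pain is a validated scale that ranges from 0-100mm". It then gives the response instruction: "Subjects are asked to draw a vertical line on the scale that corresponds to their level of pain during the procedure".

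The next sentence deals with baseline: "Baseline scores will be collected on the day of the procedure in the research office after obtaining consent". It gives no response mode. The paragraph continues: "Patients will then be asked to circle the pain scores that corresponded to the pain experienced during the procedure". It closes by saying that staff collect this reading after the procedure, once the patient is dressed.

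Elsewhere the instrument is a VAS at both times. Interventions and Interactions has patients complete an anxiety scale "and a VAS for pain" (Figure 2) after consent. The text under Group 2: Control says "After the procedure and once participants are dressed, they will fill out a 2", and the sentence goes on to name a second pain VAS. Table 1 lists VAS Pain #1 at baseline and VAS Pain #2 after the procedure.

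On analysis, the Analytical Plan says: "Regression analyses will be performed to test the hypotheses about treatment effects on primary and secondary outcomes". It allows adjustment for prognostic variables as needed and gives first-time versus repeat status as the example. It does not mention baseline pain.

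**The concern.** A line on a VAS is scored by measuring a distance in mm. Circling scores presupposes discrete printed values. The paragraph asks for both and gives no rule for turning a circle into mm. If a patient circles part of a line, someone must decide what number to enter. Data are first recorded on paper, and the response mode cannot be recovered once the form is complete.

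The circling sentence is an operating instruction. It describes how VAS Pain #2 is obtained, which is the reading that answers the first secondary objective.

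Two related gaps sit beside it. The only line-drawing instruction asks about pain during the procedure, which cannot apply to a form completed in the research office beforehand, so the question put at baseline is undefined. And baseline pain is collected from every patient without the plan saying how it will be used.

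**Working it through.** The plan gives no figure for pain, so the check is mainly a comparison of texts.

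**1. The plan's only computed figure.** The Sample Size section gives n = 80 and 80% power for a 12 mm difference in anxiety, SD 18.8, at 0.05 (taken here as two-sided). With patients treated as independent, n per arm = 2 × (1.960 + 0.842)² × 18.8² / 12² = 2 × 7.85 × 353.44 / 144 = 38.5, rounded up to 39. The t-test version needs 39.5, so 40 per arm or 80 in total, with power 80.5%. The figure reproduces. It concerns anxiety only and does not depend on how pain is recorded.

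**2. The places that describe pain recording.**

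| Place | Time point | Instrument or response |
|---|---|---|
| Secondary Objectives | During injections | VAS |
| Interventions and Interactions | Baseline | VAS, Figure 2 |
| Group 2: Control, later text | After procedure, once dressed | Second VAS |
| Table 1 | Baseline; post-procedure | VAS Pain #1; VAS Pain #2 |
| Procedure-pain paragraph, line sentence | Pain during the procedure | Draw a vertical line |
| Procedure-pain paragraph, baseline sentence | Baseline | No mode stated |
| Procedure-pain paragraph, circle sentence | Pain during the procedure | Circle scores |

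**3. Where the conflict lies.** The line sentence and the circle sentence both refer to pain during the procedure. The contradiction is therefore within the post-procedure reading. Every other entry that names an instrument names a VAS, so the circle sentence is the outlier.

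**4. Comparison with the other scales.** The anxiety and satisfaction descriptions give only the line instruction. The staff Burnout Battery, described in the same section, is circled because it shows seven discrete batteries. Pain is the only patient scale with both instructions.

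**5. Use of baseline pain.** Change from baseline is defined for anxiety, not for pain. Let ρ be the correlation between baseline and post-procedure pain. With independent patients, adjusting for baseline multiplies the residual variance by about 1 − ρ². The documents give no value for ρ. If ρ is near 0 the factor is near 1 and little is gained, but little is lost. With equal SDs at the two times, a change score would multiply the variance by 2(1 − ρ), which exceeds 1 whenever ρ is below 0.5. That favors using baseline as a covariate rather than by subtraction.

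**The case against.** The strongest reply is that this is one loose verb. The objective, the visit description, Table 1 and the opening of the paragraph itself all name a VAS. Circling may have been carried over from the Burnout Battery, though this cannot be confirmed. Figure 2 might settle the format. It is not visible in the text reviewed, and that is no fault of the plan. Nothing suggests that the arms receive different forms, so post-procedure pain would be compared on a common scale whichever mode is used. All of this stands and limits the size of the point. It does not remove the contradiction in the written instruction.

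Three stronger readings are tempting, and the documents support none of them.

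- *Baseline is a drawn line and post-procedure pain a circled category, so the two are on different scales.* The line sentence itself refers to procedure pain, the baseline sentence states no mode, and the same VAS is named at both times.
- *Because allocation is by week, the response mode could become mixed with treatment.* That would need instructions to vary by week in step with arm. Patients complete the form themselves, and nothing indicates such variation.
- *Circling costs material precision.* This needs an assumed scale. If scores were 0-10 integers in 10 mm steps, rounding would add variance of 100/12 = 8.3 mm². That is 8.3/353.4 = 2.4% at an assumed SD of 18.8 mm, and 3.7% to 0.9% over assumed SDs of 15 to 30 mm. Precision is not the reason to act.

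It can also be said that baseline adjustment is a separate matter from the draw-or-circle wording. That is fair. It is included because it uses data the trial already collects and concerns the same outcome.

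**Conclusion.** The procedure-pain paragraph contradicts itself on how one reading is recorded, and it leaves a circled response without a defined value in mm. This rests on the text alone and needs no assumption about Figure 2. It reaches all post-procedure pain readings, about 80, in one secondary outcome.

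It is a minor inconsistency. Neither a difference in scale between the two time points nor a difference between arms is shown. The primary outcome, sample size and allocation are untouched, and no numerical bias follows. The undefined baseline question and the unnamed baseline covariate are small gaps in the same outcome. The benefit of the covariate depends on ρ, which is unknown and may be low if pain before the procedure says little about pain during it.

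**What to change.** 1. In the procedure-pain paragraph, replace the circling sentence with: *After the procedure, once dressed, patients will draw a vertical line on the same 0-100 mm pain VAS (Figure 2), scored in mm.* Keep pain felt during the procedure as what the post-procedure item asks about.
2. Check that the Figure 2 form matches this at both time points.
3. Word the baseline item as current pain, since it is completed before any procedure.
4. In the Analytical Plan, state that post-procedure VAS pain is compared between arms by regression with baseline VAS pain as a covariate.

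The cost is a few sentences and one form check. No extra patients, visits, measurements or staff time are needed. The wording and form changes should be made before pain data are collected, or as early as possible if collection has begun, and the covariate should be named before the data are analyzed.
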